10.2 Analysis Populations

Three analysis sets will be defined in accordance with the consolidated ICH E6 GCP guidelines ([1](#)).

The Full Analysis Set (FAS) will comprise all enrolled patients who have received at least one dose of IMP. The FAS will be used for evaluation of safety and PD endpoints. The patients in the FAS will contribute to the analyses as allocated to treatment.

The DLT analysis set will comprise all patients in the FAS. Patients who did not complete Cycle 1 (i.e. minimum 2 infusions of Sym004 in combination with FOLFIRI [full dose]) for reasons other than drug toxicity will be excluded from the DLT analysis set. The DLT analysis set will be used for evaluation of DLTs.

The PK analysis set will comprise all enrolled and exposed patients in the dose-escalation with at least one evaluable PK profile. For a PK profile to be evaluable at least 3 measurements after C_{max} and with a negative slope on the concentration-time curve are required.

The PK analysis set will be used for evaluation of PK. For the evaluation, patients, full profiles, or single measurements can be excluded from the analyses. The decision to exclude patients, full profiles or part of profiles will be described in the Clinical Trial Report (CTR).

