6.3.1 Withdrawal from Treatment with Sym004 and/or FOLFIRI

The patient must be withdrawn from treatment with Sym004 and/or FOLFIRI in the event of any of the following:

- A DLT considered by the Investigator to require treatment discontinuation (See [Section 9.5](#)) (dose-escalation cohorts only)
- Occurrence of an AE considered by the Investigator to require treatment discontinuation
- CTCAE Grade 4 skin toxicity (applies to Sym004 only)
- FOLFIRI-related toxicity not controlled by dose-reduction guidelines are outlined in [Table 7](#) in [Section 7.2.1.1](#) and [Appendix 2](#)
- PD, verified by CT/MRI according to RECIST v1.1 ([Appendix 1](#))
- Treatment failure not meeting the criteria for PD, but considered by the Investigator to require treatment discontinuation
- Requirement for a significant surgical procedure

NOTE: Patients requiring a minor surgical procedure (e.g., port placement, skin abscess drainage) may continue at the Investigator's discretion following discussion with the Sponsor or designee. A brief interruption in therapy may be considered
- An intercurrent illness which, in the opinion of the Investigator, would prevent completion of trial-related evaluations
- The Investigator judges it necessary due to medical reasons
- Use of prohibited concomitant medication, as defined in [Section 7.5.2](#)
- Pregnancy

- Significant deviation from the protocol or eligibility criteria. Such patients will be considered protocol violations and may be discontinued from treatment after discussion with the Sponsor
- Noncompliance with trial procedures may require discontinuation after discussion with the Sponsor
- Patient withdrawal of consent and election to discontinue treatment. (Patients may leave the trial at any time for any reason if they wish to do so, without any consequences)
- Termination of the trial by the Sponsor

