6.4 Replacement of Patients

6.4.1 Dose-Escalation Phase

Patients who do not complete Cycle 1 as defined in [Section 9.5.2](#), for reasons other than DLTs, can be replaced.

Data from these patients will be included in the safety analysis, but will not contribute to the determination of the MTD.

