9.5 Dose-Limiting Toxicities

9.5.1 Definition of Dose-Limiting Toxicities

A DLT is defined as any of the following toxicities that occur during the DLT observation period, if considered by the Investigator, and confirmed by the ISMC, to be related to Sym004 or the Sym004/FOLFIRI combination:

1. Grade 3 non-hematologic toxicity regardless of duration, with the exceptions of:
 - a. Grade 3 nausea, vomiting, diarrhea, or fatigue lasting ≤ 5 days with best supportive care
 - b. Grade 3 asymptomatic electrolyte abnormalities¹
2. Any Grade 4 non-hematologic toxicity
3. Neutropenia that is:
 - a. Grade 3 or 4, associated with fever (ANC < 1000 per mm^3 ; temperature $> 38.5^\circ\text{C}$), and requiring antibiotic therapy
 - b. Grade 4 and sustained (i.e., ANC < 500 per mm^3 , duration > 5 days)
4. Thrombocytopenia that is Grade 4 (platelets $< 25,000$ per mm^3)
5. Inability to complete Cycle 1 at the initial assigned doses of Sym004 and FOLFIRI due to \geq Grade 3 toxicity
6. Treatment delays > 2 weeks from the scheduled “next doses” due to \geq Grade 3 toxicity

¹ In addition to the scheduled ECGs (at screening and EOT), an ECG should be performed as soon as possible in the event of \geq Grade 3 hypomagnesemia, and as otherwise clinically indicated. Furthermore, in the event of QT prolongation, an ECG is to be performed prior to the next dose of Sym004. See [Section 7.2.5](#) for further details regarding procedures to address this expected AE.

[Section 12.1](#) outlines the responsibilities of the ISMC with respect to DLTs.

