9.5.2 Observation Period for Dose-Limiting Toxicities

Throughout the dose-escalation phase, the decision to dose-escalate is based on close monitoring of safety during the observation period for DLTs, defined as Cycle 1, i.e. the initial 28 day period (± 2 days) from first treatment of Sym004 in combination with FOLFIRI.

A minimum of 2 infusions of Sym004 in combination with FOLFIRI (full doses) must have been administered for a patient to have completed and tolerated the DLT observation period.

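### Sections 10.2 and 6.4.1 decide who counts for DLT by the reason for not completing Cycle 1, with no exception for a patient who already had a confirmed DLT

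*Protocol*

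**What the plan says.** Three sections decide whether a dose-escalation patient counts.

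- Section 10.2 starts the DLT analysis set from the FAS, then states that those who did not receive at least two full-dose infusions of the combination "for reasons other than drug toxicity will be excluded from the DLT analysis set". It adds: "The DLT analysis set will be used for evaluation of DLTs".
- Section 6.4.1 says that patients who do not complete Cycle 1 "for reasons other than DLTs, can be replaced". It continues: "Data from these patients will be included in the safety analysis, but will not contribute to the determination of the MTD".
- Section 9.5.2 sets the completion standard that both rely on: "A minimum of 2 infusions of Sym004 in combination with FOLFIRI (full doses) must have been administered".

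Three other places work by event.

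- Section 9.5.1 defines a DLT as "any of the following toxicities that occur during the DLT observation period", if judged related by the Investigator and confirmed by the ISMC. Completing the cycle is not a condition.
- Section 7.1.4.3 expands a cohort when 1 of 3 patients has a DLT and declares the MTD exceeded when 2 or more of up to 6 do. Only its zero-DLT limb is worded in terms of patients who completed Cycle 1.
- Section 10.3.1 lists every DLT event by cohort and patient, and defines the MTD as the highest dose with at most 1 of 6 patients affected.

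**The concern.** The usual purpose of such an exclusion is to remove patients who were not observed long enough to be called DLT-free. A patient who has had a DLT needs no further observation, because the outcome is known. A rule that looks only at why the second dose was missed removes both kinds of patient.

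The case can arise under the protocol's own rules. Section 6.3.1 requires withdrawal for "A DLT considered by the Investigator to require treatment discontinuation", so a DLT does not by itself end treatment. The same list has progression, intercurrent illness and "Patient withdrawal of consent and election to discontinue treatment" as separate reasons. The recorded reason for stopping can therefore be neither toxicity nor a DLT, even though a DLT has occurred.

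At stake are the Phase 1b primary endpoint and the MTD, which rest on counts of 0, 1 or 2 patients in cohorts of 3 to 6. The error runs in one direction, towards calling a dose tolerable.

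**Working it through.** **The plan's own figure.** The only stated figure tied to the DLT count is the 9 to 18 escalation patients in section 10.1. It reproduces as 3 dose levels × 3 = 9 and 3 × 6 = 18, with no allowance for replaced patients. It is not in dispute.

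**One patient through the text.** Suppose a related Grade 3 ALT elevation on Day 9, confirmed by the ISMC, and consent withdrawn on Day 13.

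1. Section 9.5.1, item 1: this is a DLT. The exceptions cover short-lived nausea, vomiting, diarrhea or fatigue, and asymptomatic electrolyte abnormalities, not ALT.
2. Appendix 2 allows treatment to continue through isolated Grade 3 laboratory abnormalities of this kind, so the DLT need not be why the Day 15 dose is missed.
3. Section 9.5.1, item 5, does not help: it covers inability to complete Cycle 1 because of Grade 3 or higher toxicity, and here the cause is withdrawn consent.
4. Section 10.2: one infusion, non-toxicity reason, so excluded.
5. Section 6.4.1: does not count for the MTD and may be replaced.
6. Section 7.1.4.3: has had a DLT, so counts.

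Steps 4 and 5 contradict step 6, and no section says which prevails.

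**Effect on the decision if the patient is replaced by one without a DLT.**

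| Cohort | Counted by event (7.1.4.3) | Counted by reason (10.2, 6.4.1) |
|---|---|---|
| One DLT, in the patient who left | 1 of 3: three more patients | 0 of 3: escalation may proceed |
| Two DLTs, one in the patient who left | 2 of 6: MTD exceeded | 1 of 6: compatible with the MTD |

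**Effect on the reported rate.** Take a cohort of 6 with two DLTs, one in the patient who left. Without replacement, the rate is 2/6 = 33% by event and 1/5 = 20% by reason. With a DLT-free replacement, it is 2/7 = 29% if everyone counts and 1/6 = 17% under 10.2.

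**Illustrative probabilities.** Let p be the true DLT rate and q the share of DLT patients who are lost and replaced. Both are assumptions.

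- Counted rate: p′ = p(1 − q)/(1 − pq)
- Chance of clearing the dose: (1 − p′)³ + 3p′(1 − p′)² × (1 − p′)³
- Chance of at most 1 DLT in 6: (1 − p′)⁶ + 6p′(1 − p′)⁵

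Example with p = 0.33, q = 0.20: p′ = 0.264/0.934 = 0.283.

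| p | q | p′ | Clears the dose | At most 1 of 6 |
|---|---|---|---|---|
| 0.33 | 0 | 0.330 | 0.434 | 0.358 |
| 0.33 | 0.10 | 0.307 | 0.480 | 0.405 |
| 0.33 | 0.20 | 0.283 | 0.530 | 0.458 |
| 0.33 | 0.30 | 0.256 | 0.586 | 0.519 |
| 0.50 | 0 | 0.500 | 0.172 | 0.109 |
| 0.50 | 0.20 | 0.444 | 0.242 | 0.171 |

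The q = 0 rows are what the protocol would deliver if every confirmed DLT counted.

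**The case against.** The strongest reply is that other parts of the protocol would catch the event. Two limbs of 7.1.4.3 count it, 10.3.1 lists it, 6.4.1 keeps the data in the safety analysis, and section 12.1 has the ISMC consider all reported AEs and decide on escalation and the MTD by consensus. A reader might infer from 10.2 and 6.4.1 that the DLT vanishes from the trial; the documents do not support that. The loss is confined to the DLT analysis set and the MTD sentence in 6.4.1. Within those limits the problem stands: the ISMC may count the event, but no text makes it do so, and 6.4.1 says such data do not contribute.

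A reader might also infer that the patient is always replaced. Section 6.4.1 only permits it; the exclusion in 10.2 is the automatic part.

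The window is narrow. A DLT after the second full dose is unaffected. Many earlier DLTs would themselves prevent a full second dose: Grade 3 skin toxicity delays Sym004 (7.1.5.2), and low counts or unresolved gastrointestinal toxicity delay FOLFIRI (7.2.1.1). Those patients miss the dose because of toxicity and stay in the set. Progression before Day 15 should be uncommon, since the first scheduled response scan is at the end of Cycle 2 and entry requires a life expectancy above 3 months. This all stands, and it makes the larger values of q hard to defend: q applies to all DLT patients, and the model treats every affected patient as excluded and replaced.

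Finally, Amendment 3 stopped enrollment and declared the objectives no longer applicable (sections 4.1 and 5.5). An ongoing risk of escalating past a toxic dose is therefore not supported for this version. However, 10.2 and 10.3.1 are not marked as omitted, unlike 10.4.3 and 10.4.4, and 10.6 still refers to completing DLT evaluation, so the set definition still governs any reported DLT table.

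**Conclusion.** Wrong as written; low to moderate severity. Sections 10.2 and 6.4.1 apply the exclusion to patients whose DLT outcome is already known, and they contradict 7.1.4.3 and 9.5.1. The direction of the bias is certain: the count can only fall. The consequence of one lost DLT is also certain where it occurs, since it can move 1 of 3 to 0 of 3 or 2 of 6 to 1 of 6.

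How often it would occur is unknown. The probabilities above show sensitivity to assumed p and q and are not estimates for this trial. The conclusion rests on the wording, not on them. With enrollment stopped, what remains is mainly the numerator and denominator of the reported DLT summaries and any MTD statement drawn from them.

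**What to change.** Section 10.2: state that any dose-escalation patient with a confirmed DLT stays in the DLT analysis set, whatever the reason for not completing Cycle 1, and that the exclusion for an incomplete cycle applies only to patients without a DLT.

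Section 6.4.1: state that only patients without a DLT may be replaced and left out of the MTD determination, so that it agrees with 7.1.4.3. While editing, use one term for the reason in both sections. At present 10.2 refers to drug toxicity and 6.4.1 to DLTs, so a patient who stops for a toxicity that is not a DLT stays in the set under one and is replaceable under the other.

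Section 10.7 already allows such a change through an amendment, the SAP or the trial report. Because enrollment has ended, the report should also say whether any patient was affected and, if so, give the cohort's DLT count both ways.

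The cost is wording only, with no added patients, visits or data. The reported DLT rate may be slightly higher.

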10.3 Primary Endpoint and Analysis

10.3.1 Dose Escalation Phase

The primary objective of the dose-escalation phase is to determine the MTD of Sym004, assessed by the occurrence of DLTs during the DLT observation period for each of the Sym004 dose levels given in combination with FOLFIRI.

All DLT events (if any) will be listed by dose cohort and patient. A summary table of DLTs by System Organ Class (SOC) and preferred term will be presented for each dose cohort, if applicable. The summaries will include number of DLTs and number and percentages of patients who experienced a DLT. The definition of a DLT is included in [Section 9.5.1](#). The MTD is defined as the highest dose with a maximum of 1 out of 6 patients experiencing a DLT. The MTD might not be found.

10.3.2 Dose Expansion Phase

The primary objective of the dose-expansion phase is to evaluate the antineoplastic effect of Sym004. This will be evaluated by confirmed OR (i.e. documented PR or CR).

Number and percentages of patients in the FAS with confirmed OR will be presented including corresponding 95% exact Confidence Intervals (CI).

10.4 Secondary Endpoints and Analyses

All statistical analyses of the secondary endpoints for both phases will be performed after completion of the dose expansion phase of the trial.

10.4.1 Safety Endpoints and Analyses

The safety endpoints are presented below and will all be presented for the FAS by trial phase. Safety data will only be presented descriptively, and no formal statistical analyses will be performed.

10.4.1.1 Adverse Events

The AEs will be coded using Medical Dictionary for Regulatory Activities (MedDRA) current version. AEs will be regarded as treatment emergent AEs (TEAEs) if they occur after first treatment. Non-treatment emergent AEs (Non-TEAEs) are defined as AEs collected before dosing. TEAEs will be presented by SOC and preferred term unless stated otherwise. The frequencies of TEAEs will be presented including number and percentages of patients having experienced an event and the total number of events.

AEs including SAEs are reported from signing the informed consent until the end of trial participation. SAEs reported outside the required reporting window are only entered into the safety database and will be described separately in the report.

NOTE: Patients who sign the informed consent and are subsequently deemed to be screening failures will be followed for the occurrence of SAEs/AEs until it is determined they will not be participating in the trial.

All AEs will be listed. The TEAEs will be presented using summary tables by trial phase including:

- AEs, in total and sorted by frequency
- AEs by relationship
- AEs by CTCAE Grade and max CTCAE Grade
- Skin toxicity AEs defined as AEs within a predefined set of preferred terms (list to be included in the Statistical Analysis Plan [SAP])
- AEs of Medical Interest
- SAEs, in total, and by relationship
- AEs leading to withdrawal from treatment
- AEs leading to trial drug interruption or dose reduced
- Fatal AEs

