5.3.1 Screening

When the trial site identifies a patient suitable for screening, the Sponsor or designee should be contacted to ensure that a cohort is open for inclusion. Once confirmed, the patient may be approached for informed consent. Screening activities may begin only once written informed consent has been obtained.

All patients giving informed consent to participate in the trial will receive a unique patient number. This number is composed of a four-digit prefix, which identifies the site, and a three-digit number, allocated sequentially starting from 001 for the first patient screened at the site, 002 for the second patient screened etc.

The trial site staff must complete an allocation form, stating at minimum the allocated patient number and date of birth, along with the planned dates of screening and the day of first scheduled Sym004 and FOLFIRI administration (Cycle 1/Day 1, in the following C1/D1). The planned date of C1/D1 will need to be agreed upon in collaboration with the Sponsor or designee for the dose-escalation cohorts, in order to ensure adequate time between dosing of the first patient and dosing of subsequent patients in each cohort. The completed allocation form will then be sent to the Sponsor or designee prior to or on the day of Screening.

All screening activities must be performed within 14 days prior to C1/D1, unless otherwise specified. A Computed Tomography (CT) scan or Magnetic Resonance Imaging (MRI) performed within 28 days prior to C1/D1 may be used for evaluation of eligibility, provided that the scan has been performed according to protocol requirements. In the event a tumor biopsy is required for eligibility, informed consent may be obtained outside the 14-day screening period prior to C1/D1 to allow adequate turnaround time for receipt of results.

Individual screening assessments may be repeated prior to C1/D1, if justified and documented by the Investigator.

Once eligibility has been confirmed in accordance with the inclusion and exclusion criteria, the allocation form will be fully completed and signed by the Investigator and resent to the Sponsor or designee. A copy of the fully executed allocation form will be returned to the trial site for archiving. This form documents the allocated dose of Sym004.

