9 ADVERSE EVENTS

9.1 Definitions of Adverse Events

9.1.1 Adverse Event

An AE is any untoward medical occurrence in a patient or a clinical investigation subject administered a pharmaceutical product and which does not necessarily have a causal relationship with this treatment. An AE can therefore be any unfavorable and unintended sign (including an abnormal laboratory finding, symptom, or disease temporally associated with the use of an IMP, whether or not considered related to the IMP.

Please Note: Progression of disease will not be captured as an AE/SAE unless the nature of the PD is different than expected (i.e. other diagnoses and/or signs/symptoms that are not typical of PD). Events associated with the actual PD will also be captured, as determined by the investigator. Additionally, AE occurring simultaneously with PD, but which may not be related to the actual PD, will also be captured.

Causality for the above-mentioned AE will be assessed appropriately as; Related to Study Drug, Not Related to Study Drug or Related to Disease Progression. In addition, any AE, regardless of causality, that also meets seriousness criteria, will be reported on an SAE Form

Events not to be considered as Adverse Events

A pre-existing condition (i.e., a disorder that is present before the AE recording period starts and is noted on the medical history/physical examination form) should not be recorded as an AE unless the condition worsens or episodes increase in frequency during the AE recording period.

Diagnostic and therapeutic non-invasive and invasive procedures, such as surgery, should not be recorded as AEs. A medical condition for which an unscheduled procedure was performed, should however be recorded if it meets the definition of an AE. For example, an acute appendicitis should be recorded as the AE and not the appendectomy.

Procedures to support the treatment regimens, such as insertion of central venous catheters etc. should not be recorded as AEs, unless the procedures result in complications.

Events such as lab results reported outside the normal range and determined to be clinically insignificant by the Investigator will not be recorded as AEs.

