9.2 Adverse Event Recording and Reporting Instructions

9.2.1 Adverse Event Recording Period

All AEs will be recorded from signing the informed consent. The recording period ends at the time of the 1M FUP Visit.

NOTE: Patients who sign the informed consent and are subsequently deemed to be screening failures will be followed for the occurrence of SAEs/AEs until it is determined they will not be participating in the trial.

The Investigator must record all directly observed AEs and all AEs spontaneously reported by the patient. A general, open-ended type of question should be used to elicit a response from the patient, such as, “Do you have any health problems?” or “Have you had any health problems since your last visit?”.

All AEs that occur in patients during the AE recording period must be recorded/entered on the AE section of the Case Report Form (CRF), whether or not the event is assessed as related to Sym004. If the AE is serious, the SAE report forms must also be completed and submitted (see [Section 9.3](#)).

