9.2.3 Intensity

The Investigator will use CTCAE version 4.03 to describe the severity of an AE. If the severity of an AE is not specifically graded by the CTCAE guidance document, the Investigator should use the general definitions of Grades 1 to 5 as per the following, and use his/her best medical judgment to describe the severity of the AE:

- Grade 1: Mild
- Grade 2: Moderate
- Grade 3: Severe
- Grade 4: Life-threatening or disabling
- Grade 5: Death caused by the event

Changes in severity of AEs will be recorded.

Generally, an AE of CTCAE Grade 4 or 5 qualifies for SAE reporting to the Sponsor or designee. However, a laboratory abnormality of CTCAE Grade 4 does not need to be reported as an SAE, unless it meets one of the seriousness criteria in [Section 9.1.4](#).

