9.2.5 Outcome

Outcome of the AE must be assessed by the Investigator utilizing one of the following terms:

- Recovered
- Recovered with sequelae (if recovered with sequelae, specify sequelae)
- Not recovered
- Fatal
- Unknown

Instructions for reporting changes in an ongoing AE during a patient's participation in the trial are provided in the instructions that accompany the AE CRF pages.

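### Read literally, the TEAE definition leaves out of the AE summary tables any event that arises between consent and first dose and then worsens on treatment

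*Protocol*

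**What the plan says.** Three sections of the protocol bear on this.

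- **When recording starts.** Section 9.2.1: "All AEs will be recorded from signing the informed consent". Section 5.3.1 sets the usual length of the pre-dose window: "All screening activities must be performed within 14 days prior to C1/D1, unless otherwise specified". It lets consent be taken earlier when a biopsy is required for eligibility.
- **What counts as treatment-emergent.** Section 10.4.1.1: "AEs will be regarded as treatment emergent AEs (TEAEs) if they occur after first treatment". The complement follows directly: "Non-treatment emergent AEs (Non-TEAEs) are defined as AEs collected before dosing".
- **What is tabulated.** The same section: "All AEs will be listed. The TEAEs will be presented using summary tables by trial phase including". The list that follows covers frequency, relationship, grade and maximum grade, skin toxicity, events of medical interest, SAEs, withdrawals, interruptions or reductions, and fatal events.

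Three further provisions affect how the rule works. Section 9.1.1 says that a condition present before AE recording starts "should not be recorded as an AE unless the condition worsens or episodes increase in frequency during the AE recording period". Section 9.2.3 adds: "Changes in severity of AEs will be recorded". Section 9.2.5 leaves the "Instructions for reporting changes in an ongoing AE" to material that accompanies the CRF pages and is not part of the protocol.

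**The concern.** A treatment-emergent definition normally has two limbs: new onset after first dose, and worsening after first dose of something already present. Section 10.4.1.1 states only the first limb, and its second sentence appears to close off the other by assigning every event collected before dosing to the non-emergent group.

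If an event begins as Grade 1 during screening and becomes Grade 3 on treatment, the grade increase is the information that a safety table exists to show. Under the literal rule that event is missing from the grade, maximum-grade, SAE, withdrawal, dose-change and fatal-event tables alike. Under Amendment 3 only the clinical safety-related evaluations continue (Section 4.4), so these tables are a main product of the trial.

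The protocol defers the list of skin-toxicity terms to the SAP but fixes the TEAE rule itself. This is therefore a stated rule that is incomplete, not a detail left for later.

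**Working it through.** The plan gives no figure to reproduce, because the point concerns a definition. The check is to follow one clinical course, Grade 1 rising to Grade 3 after first dose, through the protocol's rules and vary only when the event began.

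| Onset | How it is recorded | Status under 10.4.1.1 | Where it appears |
|---|---|---|---|
| Before consent | Medical history; becomes an AE when it worsens (9.1.1), here after dosing | TEAE | AE tables and listings |
| Between consent and first dose; worsening noted as a severity change on the existing record | AE at onset (9.2.1); grade change added (9.2.3) | Non-TEAE | Listings only |
| Between consent and first dose; worsening opened as a new record | AE at onset; second record after dosing, if the CRF instructions say so (9.2.5) | Second record is a TEAE | AE tables and listings |
| After first dose | AE at onset | TEAE | AE tables and listings |

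**Inconsistency.** The first and second rows are the same event with onsets perhaps a day apart, on either side of consent, and they are treated differently. The rule in 9.1.1 does not rescue the second row, since it covers only conditions that precede the recording period. A pre-consent condition that first worsens during screening becomes an AE before dosing and so moves into the second or third row as well.

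**Dependence on the CRF.** The second and third rows differ only in a data-entry convention that the protocol does not state. The same patient could be in or out of the tables according to that convention.

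**Direction.** The literal rule can drop on-treatment worsening. It cannot add any. Compared with a definition that includes worsening, it gives the same count or a lower one.

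**Plausibility.** Exclusion criterion 15b in Section 6.2 bars diarrhea of Grade 2 or above in the 2 weeks before C1/D1. Grade 1 diarrhea that appears in screening does not exclude a patient under that criterion, and the protocol treats diarrhea as important enough to require prophylaxis (Section 7.2.3.2).

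**Size.** The protocol gives no rate of screening-onset events, so no expected undercount can be derived. Only the weight of one missed patient in a given row of a table can be shown, using the planned sizes in Section 10.1:

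- Escalation, 9 to 18 patients: 1/18 = 5.6% to 1/9 = 11.1%.
- Expansion, 32 to 41 patients: 1/41 = 2.4% to 1/32 = 3.1%.

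These figures are illustrative only. Section 5.5 says that accrual has stopped and the planned total will not be reached, so the actual denominators will differ.

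**The case against.** The strongest case on the other side has four parts.

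1. **Other safety outputs do not use TEAE status.** DLTs have their own summary by cohort (10.3.1). Laboratory values, vital signs, physical and skin examination and ECG are presented separately (10.4.1.2 and 10.4.1.3), and all AEs are listed. This stands. A reader might infer that worsened events disappear from every safety summary in the report, but the documents do not support that. The other outputs are not full substitutes, however. The DLT table covers only Cycle 1 of the escalation phase, and Grade 3 diarrhea of 5 days or less is an exception under the first DLT criterion (9.5.1).

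2. **The exclusion is not certain.** If the CRF instructions open a new record when the grade changes, the existing wording already captures the worsening. This stands as a possibility, so the loss cannot be called automatic. It does not dispose of the point, because the protocol does not say which convention applies.

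3. **The affected group is small.** The window is short, the investigator rechecks eligibility before the first infusion (5.3.3), and several exclusions remove patients with more serious recent events. This stands as a limit on frequency. Low-grade events that allow entry remain, and these have the most room to worsen.

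4. **The consequences are limited.** Safety analyses are descriptive (10.4.1), and during escalation the ISMC reviews all reported AEs and SAEs, not TEAE tables (12.1). This also stands. The effect is on the end-of-trial tabulation, and nothing here suggests that dose decisions were affected. Section 10.7 would allow the SAP or the trial report to describe a change, but that is a route to the repair and not evidence that it has been made.

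**Conclusion.** The point holds for the AE summary tables in Section 10.4.1.1. Taken at its word, the definition omits an event that arises between consent and first dose and then increases in grade on treatment, and leaves it in the listings only. The conclusion rests on two assumptions: that an AE in this section means the whole episode, and that the CRF instructions do not turn a worsening into a new post-dose record.

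The size is unknown. It is probably confined to few patients, given the short window, but each would matter in a small phase, and any error is towards undercounting. The percentages above show the weight of one patient in one row. They should not be read as an estimate of bias, and a patient with any other TEAE would still count in the overall incidence.

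**What to change.** Replace the definition in 10.4.1.1 with one that has both limbs. A TEAE is an AE with onset on or after the first dose of Sym004 or FOLFIRI, or an AE present before first dose that increases in CTCAE grade or becomes serious after it, through the 1M FUP visit. Restrict the non-emergent category to the remaining pre-dose events. State that the tables use the post-dose grade, and that a worsening is analysed in this way whether it was entered as a new AE or as a severity change.

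The cost is one sentence and one derivation rule. Severity changes must already be recorded under Section 9.2.3, so the grade limb needs no new data. Section 10.7 allows the change to be documented in an amendment, the SAP or the trial report.
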